2.14 Interim analysis

Three interim analyses were planned during the study. The first interim analysis was conducted one year after the first patient has been enrolled and included a preliminary analysis on safety. The second interim analysis was conducted 12 months after LPFV in the 30% pretreated and premenopausal cohort and included a preliminary analysis on safety, efficacy and quality of life. The third interim analysis took place 6 months after the last patient had been recruited and included a preliminary analysis on safety and efficacy.

3 Sample size calculation

Sample size assumptions in this study for postmenopausal patients without prior treatment for advanced disease are based on the data from the CLEE011X2107 study (Juric, poster presented at ASCO 2016), which enrolled a similar patient population.

Regarding patients in later than first lines and pretreated premenopausal patients, assumptions are based on Cristofanilli et al 2016 - PALOMA-3 final analysis.

It is expected that the CBR (based on local assessment) by week 24 is in a range as reported for the CLEE011X2107 study for the ribociclib + letrozole group (CBR = 79%, 95% confidence interval [59% to 92%]).

Using the lower limit of the CI (59%) as a pessimistic estimate for the CBR by week 24, a sample size of 500 produces a two-sided 95% confidence interval with a width equal to 8.6 percentage points (the associated 95% CI is [54.7% to 63.3%]). When using the same CBR as observed (CBR 79%), a sample size of 500 produces a two-sided 95% confidence interval with a width equal to 7.2 percentage points (the 95% CI is [75.4% to 82.6%]). Using the upper limit of the CI (92%) as an optimistic estimate for the CBR, a sample size of 500 produces a two-sided 95% confidence interval with a width equal to 4.8 percentage points (the 95% CI is 89.6% to 94.4%). Assuming an estimated rate of 70% to be recruited in the subgroup of postmenopausal first line patients resulting in a sample size of 350 patients, the width of the confidence interval will be between 10.4 percentage points (pessimistic scenario) and 5.6 percentage points (optimistic scenario).

Regarding the subgroup of second or further treatment lines and premenopausal patients, assuming an estimated rate of 30% to be recruited, and further based on the data as presented by Cristofanili et al. (CBR 67%, 95% CI [61.3% to 71.5%]), the resulting precision based on 150 patients leads to a width of the resulting 95% confidence interval between 15.6 percentage points (pessimistic scenario) and 14.4 percentage points (optimistic scenario).

Thus, a sample size of 500 patients allows estimating the CBR in this patient population with reasonable precision.

4 Change to protocol specified analyses

Additionally to protocol specified analyses, the time to and duration of RECIST response was analysed for the full analysis set (FAS).

5 Appendix

5.1 Definition of efficacy variables

Progression:

1. ds.eotdreasn = 4 (Main reason for ribociclib discontinuation = progressive disease)
2. ds.eotprdi1n = 1 (Radiologic progression according to RECIST 1.1) OR
3. ds.eotprdi3n = 1 (Clinically symptomatic progress) OR
4. zr.recoveran = 4 (Overall lesion response = Progressive Disease) OR
5. zr.recnewln=1 (New Lesion)

Progression date:

1. ds.eotcprdt (date of clinically symptomatic progress) OR
2. Date of Evaluation where zr.recoveran = 4 or zr.recnewln = 1

Response:

3. zr.recoveran (Overall lesion response)

Assessment Date:

4. zr.tlesdt (Date of image or examination, Target Lesion Assessment)
5. zr.ntlesdt (Date of image or examination, Non-Target Lesion Assessment)
6. zr.nlesdt (Date of image or examination at which new lesion appeared)

Date of Death:

7. sc.deathdt

Date of last contact:

8. sc.eoslcdt

Start of treatment = first administration of Ribociclib or Letrozole:

9. min(min(zq.ribostdt), min(zq.letrstdt))

5.1.1 Clinical Benefit Rate (CBR) until week 24

Best overall response in (CR, PR, SD, NCRNPD):

1. zr.recoveran = 1; at least two determinations of CR at least 4 weeks apart before progression OR
2. zr.recoveran = 2; at least two determinations of PR or better at least 4 weeks apart before progression (and not qualifying for a CR)
3. zr.recoveran = 3; two determinations of SD at least 12 weeks apart (and not qualifying for PR or PD)

4. zr.recoveran = 5

Tumor evaluations are scheduled for baseline, Cycle 4 and cycle 7 etc. (every 12 weeks). Thus, to assess the CBR at week 24 the first two post-baseline evaluations have to be considered. Additionally it has to be checked that no progression occurred during the following 4 weeks. Deviations against the time schedule is investigated and assessed during the data review meeting.

5.1.2 Overall response rate (ORR) by week 24

Similar to 5.1.1, but the best overall response must be in in (CR, PR)

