2. =After the last adequate tumor assessment. "Date of next scheduled assessment" is defined in [Section 3.2.7](#).

3. =The rare exception to this is if the patient dies no later than the time of the second scheduled assessment as defined in the protocol in which case this is a PFS event at the date of death.

The primary analysis and the sensitivity analyses must be specified in the protocol. Clearly define if and why options (1) are not used for situations C, E and (if applicable) F.

Situations C (C1 and C2): Progression or death after one or more missing assessments: The primary analysis is usually using options (1) for situations C1 and C2, i.e.

- (C1) taking the actual progression or death date, in the case of only one missing assessment.
- (C2) censoring at the date of the last adequate assessment, in the case of two or more consecutive missing assessments.

In the case of two or missing assessments (situation C2), option (3) may be considered jointly with option (1) in situation C1 as sensitivity analysis. A variant of this sensitivity analysis consists of backdating the date of event to the next scheduled assessment as proposed with option (2) in situations C1 and C2.

Situation E: Treatment discontinuation due to ‘Disease progression’ without documented progression: By default, option (1) is used for situation E as patients without documented PD should be followed for progression after discontinuation of treatment. However, option (2) may be used as sensitivity analysis. If progression is claimed based on clinical deterioration instead of tumor assessment by e.g. CT-scan, option (2) may be used for indications with high early progression rate or difficulties to assess the tumor due to clinical deterioration.

Situation F: New cancer therapy given: the handling of this situation must be specified in detail in the protocol. However, option (1), i.e. censoring at last adequate assessment may be used as a default in this case.

Additional suggestions for sensitivity analyses

Other suggestions for additional sensitivity analyses may include analyses to check for potential bias in follow-up schedules for tumor assessments, e.g. by assigning the dates for censoring and events only at scheduled visit dates. The latter could be handled by replacing in [Table 3-2](#) the “Date of last adequate assessment” by the “Date of previous scheduled assessment (from baseline)”, with the following definition:

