1.2 Study objectives and endpoints

Objectives and related endpoints are described in the table below (in accordance with Table 3-1 from the protocol).

Primary Objective	Endpoint

The primary objective of this study is the assessment of the clinical benefit rate after 24 weeks for the total population and for cohorts A and B separately:
 
1. Cohort A: postmenopausal women and men who received no prior treatment for advanced disease. (70% group)2. Cohort B: pre-, and perimenopausal women who received no prior treatment for advanced disease as well as pre-, peri- and postmenopausal women and men who received no more than 1 prior chemotherapy and 2 prior lines of endocrine therapy for advanced disease (30% group)	Clinical Benefit Rate (CBR) after 24 weeks of treatment as defined by RECIST 1.1 as percentage of patients with CR, PR or SD until week 24 or longer as well as patients with NCRNPD >24 weeks for patients with non-measurable disease

Secondary Objectives	Endpoint

To assess the clinical benefit rate (CBR) after 24 weeks among Cohort B1 and B2:
	
Clinical Benefit Rate (CBR) after 24 weeks of treatment as defined by RECIST 1.1 as percentage of patients with CR, PR or SD until week 24 or longer as well as patients with NCRNPD >24 weeks for patients with non-measurable disease

Progression-free survival (PFS) for the three different populations: Cohort A, Cohort B1, Cohort B2
	
PFS based on radiologic assessment by investigator using RECIST 1.1 criteria (e.g. median PFS, PFS rate at 12 and 18 months)

Overall survival (OS) for the three different populations, defined as the time from date of start of treatment to date of death due to any cause.
	
Overall survival (OS) (e.g. OS rate at 12 and 24 months)

Overall response rate (ORR) for the three different populations, defined as complete response or partial response as defined by RECIST 1.1
	
Overall Response Rate (ORR) after 24 weeks

To evaluate the safety and tolerability of ribociclib in combination with letrozole (and goserelin in premenopausal patients)
	
Frequency/severity of AEs AEs of special interest: Frequency, severity, frequency per patient, time to Event, duration of Event and recurrence

To evaluate patient reported outcomes for health related quality of life
	
Laboratory values Time to 10% deterioration in the global health status/QOL scale score of the EORTC QLQ-C30

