2.7 Analysis of secondary efficacy objective(s)

2.7.1 Secondary endpoints

2.7.2 Statistical hypothesis, model, and method of analysis

The following secondary efficacy variables were analyzed in an explorative manner for the full analysis set (FAS): overall response rate (ORR) by Week 24, progression-free survival (PFS) and overall survival (OS).

ORR within Week 24

The ORR within Week 24 was derived from the sequence of overall lesion responses as described for the primary efficacy variable. The ORR by Week 24 was summarized using frequency tables presenting absolute and relative frequencies together with appropriate confidence intervals. Furthermore, the ORR at EOT was analyzed.

Progression-free survival

Progression-free survival (PFS) is the time from date of start of treatment to the date of event defined as the first documented progression or death due to any cause. If a patient had not had an event, progression-free survival was censored at the date of last adequate tumor assessment. Disease progression for primary efficacy endpoint derivation was assessed using the local investigator's tumor assessment (treating center's radiologist). PFS was summarized using the Kaplan-Meier method. Percentiles (25%, median, 75%) of the event time distribution were presented along with their two-sided 95% confidence interval. Additionally, Kaplan-Meier estimates for the proportions of patients progression-free by Week 48 and Week 72 were presented. The Kaplan-Meier curve (with censored patients at number of patients at risk) was displayed graphically.

Overall survival

Overall survival (OS) is defined as the time from date of start of treatment to date of death due to any cause. If a patient was not known to have died, survival was censored at the date of last

contact. OS was summarized using the Kaplan-Meier method as described above. The Kaplan-Meier curve was displayed graphically. Additionally, the proportion of patients alive at 48 and 96 weeks were presented

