5.1.3 Progression-free survival

Start date = Start of treatment (first administration of Ribociclib or Letrozole)

End date = First date of progress or date of death or (if no event) date of last tumor assessment

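### SAP 5.1 and 5.1.3 program clinically symptomatic progression as a PFS event, although the stated endpoint is radiologic RECIST 1.1 progression or death and no departure is declared

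*SAP*

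**What the plan says.** **Stated endpoint.** Protocol Table 3-1 and the table in SAP 1.2 give PFS as "PFS based on radiologic assessment by investigator using RECIST 1.1 criteria". SAP 2.7.2, following protocol 10.5.1, counts first documented progression or death from any cause. It adds: "Disease progression for primary efficacy endpoint derivation was assessed using the local investigator's tumor assessment (treating center's radiologist"). For patients without an event, "progression-free survival was censored at the date of last adequate tumor assessment".

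**Programmed endpoint.** SAP 5.1 lists five items under Progression:
- the end-of-treatment reason, "ds.eotdreasn = 4 (Main reason for ribociclib discontinuation = progressive disease"), with no connector to the next item;
- an end-of-treatment flag for radiologic progression;
- "ds.eotprdi3n = 1 (Clinically symptomatic progress) OR";
- an overall lesion response of PD;
- a new lesion.

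It offers two progression dates: the date of clinically symptomatic progress, or the date of an evaluation showing PD or a new lesion. SAP 5.1.3 sets the PFS end date as "First date of progress or date of death or (if no event) date of last tumor assessment".

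**Default rule.** Table 3-2 in protocol Appendix 14.2 covers discontinuation for progression without documented progression as situation E. Its default, option 1, is to ignore the claim. Option 2 counts it as progression at discontinuation, and the text names this as a possible sensitivity analysis. Appendix section 3.2.9 instructs: "Clearly define if and why options (1) are not used for situations C, E and (if applicable) F". SAP section 4 lists only added analyses of time to response and duration of response.

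**The concern.** The text that describes PFS and the text that programs it define different events. If the datasets follow 5.1 as written, the reported curve includes investigator-judged symptomatic progression while the endpoint description says radiologic. A reader of the report would not know this, because the SAP neither declares nor explains it.

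Parts of 5.1 and 5.1.3 can also be programmed in more than one way. Two competent programmers could produce different PFS datasets from the same plan.

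**Working it through.** The documents give no PFS event count, power or share of clinical-only progression, so there is no plan figure to reproduce. The check is a comparison of rules on cases, followed by an illustration.

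**Cases (hypothetical patients, 12-weekly scans)**

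| Case | SAP 2.7.2 with the situation E default | SAP 5.1 and 5.1.3 as written |
|---|---|---|
| SD at weeks 12 and 24; clinical progression at week 30; no PD scan; new therapy | Censored, week 24 | Event, week 30 |
| PD scan at week 24; clinical progression at week 40 | Event, week 24 | Event, week 24 |
| End-of-treatment reason is progression; no PD or new-lesion evaluation; no clinical date | Censored at last adequate scan | Meets Progression but has no date: undefined |
| SD at weeks 12 and 24; UNK at week 36; then lost | Censored, week 24 | Read literally: censored, week 36 |

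- **Case 1** is the core contradiction. Under SAP 2.5.3, applied to PFS through 2.7.3, scans after a new antineoplastic drug are not used, so the two rules stay apart.
- **Case 2** shows that clinical progression after radiologic PD changes nothing, because the first date is taken.
- **Case 3** turns on 5.1.3 working with dates while the end-of-treatment reason and radiologic flag have none of their own. The first item may also be a parent condition for the next two rather than a criterion in its own right.
- **Case 4** turns on one word. Appendix 3.2.7 limits an adequate assessment to CR, PR or SD, and 3.2.8 treats non-CR/non-PD as equivalent to SD. UNK is excluded. Here the difference is 36 − 24 = 12 weeks.

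**Illustration of case 1.** Inputs from the documents are exponential PFS at the medians in protocol 1.2.6 (25.3 months first line, 5.5 months pretreated) and 12-weekly scans. Assumptions not in the documents are 52 weeks of accrual, at least 80 weeks of follow-up for every patient, and a share f of patients whose progression is clinical only and never becomes an event under the default rule. There were 400,000 simulated patients.

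Kaplan-Meier progression-free proportion at week 48:

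| | Clinical counted (5.1) | Ignored, f = 5% | f = 10% | f = 20% | f = 30% |
|---|---|---|---|---|---|
| First line | 73.8% | 74.9% | 76.1% | 78.3% | 80.7% |
| Pretreated | 24.8% | 26.3% | 28.0% | 31.6% | 35.9% |

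- The gap runs from 74.9 − 73.8 = 1.1 to 80.7 − 73.8 = 6.9 points first line, and from 26.3 − 24.8 = 1.5 to 35.9 − 24.8 = 11.1 points pretreated. At f = 0 the rules agree.
- As a check, 48 weeks is 48 × 12/52.18 = 11.04 months, and 0.5^(11.04/25.3) = 73.9%. The 5.1 rule returns the input curve because every simulated clinical progression is a true one. The gap is therefore informative censoring under the default rule. It does not show that 5.1 biases PFS.

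**The case against.** The strongest reply has four parts.

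1. **Option 2 is permitted.** Table 3-2 sets its defaults unless the protocol or analysis plan specifies otherwise, and Appendix 4.1 lets deviations be defined as late as the analysis plan. Counting clinical progression can also be the less biased choice, as the illustration shows. This stands, and the concern is not that option 2 is wrong. But SAP 1.2 and 2.7.2 still state the radiologic endpoint, and the required reason is absent.

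2. **Few patients should be affected.** Protocol 7.2.1.1 describes symptomatic progression during treatment continued after radiologic progression and requires imaging when it occurs. Protocol 7.2.1 requires RECIST documentation for patients discontinued for progression. SAP 2.5.1 sends undocumented cases to the data review meeting. This limits the number, but none of these provisions says whether a remaining case is a PFS event.

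3. **The missing adequate may be shorthand.** SAP 2.7.2 and the censoring reasons in 5.4.4 keep the term, and Appendix 4.5.1 abbreviates in the same way. A reader might infer that UNK scans will extend follow-up. The documents support that only if 5.1.3 is read literally and alone.

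4. **PFS is secondary and exploratory**, with no hypothesis or comparator. That lowers the stakes but does not remove the contradiction.

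A reader might also infer that the undated flags create events without a time. They do not clearly do so: 5.1.3 needs a date, so the status of these cases is undefined.

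**Conclusion.** The contradiction holds. Followed as written, SAP 5.1 and 5.1.3 yield a PFS that differs from the one in protocol Table 3-1, SAP 1.2 and SAP 2.7.2 for any patient with clinical progression before, or without, documented RECIST progression. The departure from the situation E default is neither declared nor explained. The undefined status of the end-of-treatment flags and the missing adequate are wording gaps to close alongside it.

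The size cannot be known from the documents. The week-48 gaps of about 1 to 7 points first line and 1 to 11 points pretreated depend on the assumed 5 to 30% share.

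Three stronger readings are not supported:
- **A stated shift in median PFS, or a bias in a known direction.** The documents give no share of clinical-only events, and which rule is nearer the truth depends on whether symptomatic progression is real progression.
- **Damage to the primary endpoint.** SAP 2.5.1 derives best response from investigator lesion responses. CBR could be touched only if the before-progression condition and the four-week check in SAP 5.1.1 use the 5.1 progression list.
- **Loss of comparability with the reference trials.** The documents do not give those trials' rules for clinical-only progression.

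**What to change.** - **SAP 5.1:** define the primary PFS event as an overall lesion response of PD or a new lesion, dated by the evaluation, or death from any cause.
- **Sensitivity analysis:** report PFS counting clinical progression (Table 3-2, situation E, option 2) under its own label, and note that ignoring it in the primary analysis may cause informative censoring.
- **If the sponsor prefers option 2 as primary:** say so, with the reason, in SAP 2.7.2 and section 4, and make the radiologic rule the sensitivity analysis.
- **End-of-treatment reason and radiologic flag:** remove them from the event definition, or give each a date and state how the first item connects to the next two.
- **SAP 5.1.1:** state which progression definition its before-progression condition and four-week check use.
- **SAP 5.1.3:** censor at the last adequate tumor assessment, listing CR, PR, SD or NCRNPD. NCRNPD should be named because patients with only non-measurable disease are eligible.

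The cost is SAP wording and one extra table. The fields are already named in SAP 5.1, so no new data collection is needed.

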5.3 Exclusion criteria

Patients eligible for this study must **not** meet **any** of the following criteria:

1. Patient with symptomatic visceral disease or any disease burden that makes the patient ineligible for endocrine therapy per the investigator's best judgment.
2. Patient who received any prior CDK4/6 inhibitor
3. Patient who received any prior mTOR-inhibitor
4. Patient has a known hypersensitivity to any of the excipients of ribociclib, letrozole (or goserelin if pre- or perimenopausal)
5. Patients with current inflammatory breast cancer (< 4 weeks before enrollment).
6. **For Cohort A:** prior treatment for advanced or metastatic disease
 - Patients who received \leq 21 days of aromatase inhibitor treatment for advanced disease prior to enrollment are eligible.

Note: Patients starting study treatment directly after any endocrine anti-cancer therapy within less than 5 half-lives of the previous therapy should be monitored closely for possible overlapping toxicities.

7. **For Cohort B:**

- Patient who has received more than one prior chemotherapy regimen for advanced breast cancer
AND/OR
- Patient who has received more than two prior hormonal therapy regimens for advanced breast cancer. (Treatment for \leq 21 days with an aromatase inhibitor for advanced disease is not considered an endocrine therapy line).

8. Patient is concurrently using other anti-cancer therapy. (Treatment with bisphosphonates or denosumab is generally not considered anti-cancer therapy).
9. Patient has had major surgery within 14 days prior to starting study drug or has not recovered from major side effects.
10. Patient has not recovered from all toxicities related to prior anticancer therapies to NCI CTCAE version 4.03 Grade \leq 1. Exception to this criterion: patients with any grade of alopecia are allowed to enter the study.
11. Patient has a concurrent malignancy or malignancy within 3 years of enrollment, with the exception of adequately treated, basal or squamous cell skin carcinoma, non-melanomatous skin cancer or curatively resected cervical cancer.
12. Patients with central nervous system (CNS) involvement unless they meet ALL of the following criteria:
 - At least 4 weeks from prior therapy completion (including radiation and/or surgery) to starting the study treatment.
 - Clinically stable CNS tumor at the time of screening and not receiving steroids and/or enzyme inducing anti-epileptic medications for brain metastases.

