2.1.1 General definitions

Study treatment: The combination of drugs including investigational drug ribociclib as well as letrozole and goserelin acetate.

On-treatment period: Period the patient was exposed to any study treatment, i.e from the first administration of any study treatment at or after C1/D1 to the last administration of any study treatment (for ribociclib and letrozole documented on the Treatment Completion CRF and for Goserelin documented on the Dosage Administration record but not later than the End-of-study visit (see 5.2.1)

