5.2 Definition of safety variables

5.2.1 Duration of study treatment exposure

For ribociclib and letrozole the duration of exposure (days) = date of last administration of ribociclib resp. letrozole – date of first administration of ribociclib resp. letrozole + 1 day. The first administration of the study treatments ribociclib and letrozole are taken from the respective Dosage Administration Record, i.e. the date of first dose > 0 at/after C1/D1. The date of last administration of the study treatments ribociclib and letrozole are taken from the Treatment Completion CRF. In case of ongoing treatment, resulting in missing end days on Treatment Completion CRF, the end date is substituted hierarchy by:

- End date of last administration with dose >0 of ribociclib resp. letrozole on the Dosage Administration record before End-of-Treatment-visit
- If the end date of the last administration with dose >0 of ribociclib resp. letrozole on the Dosage Administration is missing (normally because “ongoing” is ticked) the date of the last visit during the on-treatment period (C1/D1 to End-of-treatment) is used to substitute the end date.

For goselerin the duration of exposure (days) = date of last administration of goselerin – date of first administration of goselerin + 1 day. The first administration of the study treatment goselerin is taken from the respective Dosage Administration Record, i.e. the first dose > 0 at/after C1/D1. The end of the third component goselerin is not asked at the Treatment Completion CRF and must be derived from the Dosage Administration record therefore. Goselerin may be continued in combination with a follow-up therapy and may be documented on the Dosage Administration Record, although it is no longer a study treatment. For this reason

the date of last goselerin administration is the last dose > 0 administered until the End-of-treatment visit.

The exposure to study treatment is displayed for each of the third components separately, and in combination. For combination, called “exposure to any of the study treatments”, the first start date and the last end date of the study treatments is used for calculation.

The duration of exposure includes the periods of temporary interruption (of any component of the study treatment for any reason).

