5.4.5 Study treatment

In case of missing or partial start date, the start date should be shifted to the earliest possible date, but not earlier than the C1/D1 visit, i.e. the beginning of the on-treatment period, respectively not earlier than the previous administration. Missing or partial end dates (which result often from "ongoing" answers) should be shifted forward as far as possible: At maximum to the last documented on-treatment visit, i.e. C1/D1 to End-of-treatment-visit and not later than the following administration.

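### SAP 5.1 starts the PFS, OS and time-to-response clock at the earliest recorded ribociclib or letrozole date, without the Cycle 1 Day 1 floor that the SAP applies to exposure

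*SAP*

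**What the plan says.** **Efficacy clock.** SAP 5.1 states "Start of treatment = first administration of Ribociclib or Letrozole" and gives the derivation as "min(min(zq.ribostdt), min(zq.letrstdt" (closing brackets omitted here), which is the earlier of the first ribociclib and first letrozole start dates. SAP 5.1.3 and 5.1.4 use this date as time zero for PFS and OS. SAP 2.5.4.1 also measures time to response from start of treatment.

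**Exposure and safety clock.** SAP 2.1.1 runs the on-treatment period "from the first administration of any study treatment at or after C1/D1". For ribociclib and letrozole exposure, SAP 5.2.1 takes "the date of first dose > 0 at/after C1/D1".

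**Date imputation.** For missing or partial treatment start dates, SAP 5.4.5 says "the start date should be shifted to the earliest possible date, but not earlier than the C1/D1 visit".

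**Eligibility.** Under Protocol 5.3, criterion 6, cohort A patients who had no more than "21 days of aromatase inhibitor treatment for advanced disease prior to enrollment are eligible". Criterion 7 does not count the same lead-in as an endocrine line in cohort B. A note to criterion 6 foresees study treatment starting straight after earlier endocrine therapy and asks only for close monitoring of overlapping toxicity.

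**24-week endpoint.** SAP 5.1.1 says that "to assess the CBR at week 24 the first two post-baseline evaluations have to be considered", and adds a check for progression over the next four weeks. It names no start date.

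**The concern.** The same SAP contains two rules for when treatment starts, and only one is bounded at C1D1. The efficacy rule is the unbounded one. A patient who was already taking letrozole and simply continues it could therefore have one start date for exposure and safety and an earlier one for PFS and OS.

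Days before C1D1 cannot contain a study event. The patient has to be alive to reach C1D1, and progression is judged on scans made after baseline. Starting the clock early therefore adds event-free time to every affected patient, whether the observation ends in an event or in censoring. PFS and OS are lengthened. Time to response is lengthened too, which there looks unfavourable. In a single-arm trial read against outside results, no control arm carries the same shift.

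**Working it through.** No planning figure in either document depends on the time origin: the confidence-interval widths in Protocol 10.8 and SAP 3 need only the assumed rate and the sample size. There is thus no stated figure to reproduce. The check compares the rules and then sizes the effect.

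**1. The rules side by side**

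| SAP section | Used for | C1D1 floor | Dose above zero |
|---|---|---|---|
| 5.1, 5.1.3, 5.1.4 | PFS, OS | no | no |
| 2.1.1 | on-treatment period | yes | not stated |
| 5.2.1 | exposure | yes | yes |
| 5.4.5 | missing or partial start dates | yes | not stated |

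A complete letrozole start date before C1D1 passes through 5.4.5 untouched, is dropped by 5.2.1, and becomes time zero under 5.1.

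**2. Effect on one patient.** If the recorded date is *s* days before C1D1, PFS and OS time each increase by exactly *s* days. At the lead-in limit *s* = 21, or 21 / 30.44 = 0.69 months.

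**3. Effect on the Kaplan-Meier median.** Inputs:

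- Median PFS of 5.5 months (pretreated) and 25.3 months (first line), both from study CLEE011X2107 as reported in Protocol 1.2.6, used for illustration only. In days these are 167.4 and 770.1.
- *s* = 21 days.
- Fraction affected, *f*: not in the documents. Assumed range 10% to 100%.
- Exponential PFS: an assumption, with λ = ln 2 / median.

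With a fraction *f* shifted by *s*,

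S(t) = (1 − f)·exp(−λt) + f·exp(−λ(t − s)) for t ≥ s.

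Setting S(t) = 0.5 gives

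median = [ln 2 + ln(1 − f + f·exp(λs))] / λ.

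Pretreated example with f = 10%: λ = 0.6931 / 167.4 = 0.00414 per day and exp(21λ) = 1.091. The added time is ln(1.0091) / 0.00414 = 2.2 days, so 167.4 becomes 169.6 days, or 5.57 months.

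| f | Pretreated, true 5.50 months | First line, true 25.30 months |
|---|---|---|
| 10% | 5.57 (+1.3%) | 25.37 (+0.3%) |
| 25% | 5.68 (+3.2%) | 25.47 (+0.7%) |
| 50% | 5.85 (+6.4%) | 25.65 (+1.4%) |
| 100% | 6.19 (+12.5%) | 25.99 (+2.7%) |

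At f = 100%, the week-48 PFS estimate moves from 24.9% to 27.1% (pretreated) and from 73.9% to 75.3% (first line). With a 7-day offset and f = 100%, the medians rise by 4.2% and 0.9%.

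**4. The 24-week rate.** Under SAP 5.1.1 the two scans counted are the same whichever date starts the clock, so the offset has no effect. If a calendar cut at day 168 were used instead, the Cycle 7 Day 1 scan, 168 days after C1D1, would fall at 168 + 21 = 189 days (182 to 196 with the ±7-day scan window). It would drop out of the window, which would tend to lower the rate.

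**The case against.** The strongest reply is that the effect needs a data entry that the protocol does not ask for. Protocol 7.1.2 starts study letrozole on Day 1. Protocol 7.1.1.2 collects earlier anticancer therapy separately, with its own start and end dates. Nothing says that pre-study letrozole goes into the dosing data. The lead-in may be any aromatase inhibitor, and one other than letrozole would leave the letrozole date unaffected. PFS and OS are secondary and descriptive. All of this stands, and it makes the effect conditional.

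The floors in 2.1.1 and 5.2.1 might be read as proof that earlier records exist. They are not: the C1D1 condition may be defensive, and zero-dose rows arise from ordinary interruptions. The only non-study dosing that SAP 5.2.1 acknowledges on the dosing record is goserelin continued after study treatment.

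Two stronger readings are tempting. One is that the primary 24-week rate shares this time origin and is credited with pre-study time. The documents do not support that: SAP 5.1.1 counts scans and names no start date, and a calendar cut would push the rate down. A strict day-168 cut would also lose in-window scans in patients with no lead-in, since a scan seven days late falls at day 175. The other is that median PFS in pretreated patients is inflated by about 13%. That figure requires every such patient to carry the full 21 days, and nothing in the documents suggests it.

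The reply does not explain why the SAP bounds the start date for exposure and leaves it unbounded for efficacy.

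**Conclusion.** The inconsistency is real and can be read directly from the SAP. Its effect on PFS, OS and time to response is conditional on complete letrozole start dates before C1D1 being present in the dosing data. The documents neither show this nor rule it out.

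For each affected patient the bias equals the offset. For the population, with a 21-day offset and exponential PFS, the pretreated median of 5.50 months would become 5.57 to 6.19 months as the affected share runs from 10% to 100%; the first-line median would rise by 2.7% at most. Cohort B2, the pretreated group, is the most exposed because its expected PFS is shortest. Twenty-one days caps only the uncounted lead-in: a start date carried over from an earlier letrozole course would give a larger offset, for which the documents offer no figure.

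The primary endpoint is not shown to be touched. This is a free improvement rather than a threat to the main conclusion.

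**What to change.** In SAP 5.1, 5.1.3 and 5.1.4, define start of treatment as the first ribociclib or letrozole record with a dose above zero dated at or after C1D1, matching SAP 5.2.1. Use that date for PFS, OS and time to response.

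As a check, count the patients whose first recorded letrozole date precedes C1D1. If there are none, no PFS, OS or time-to-response figure changes on that account; if there are some, rerun these three analyses.

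The cost is one sentence of SAP text and one programming condition. It needs no new data, and I see no drawback.
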